### **8.3 Removal of Subjects from Therapy or Assessments**

Although the importance of completing the entire clinical study will be explained to the subjects, any subject is free to discontinue his/her participation in the study at any time and for whatever reason, specified or unspecified, and without any prejudice. No constraints are to be imposed on the subject, and when appropriate, a subject may be treated with other conventional therapy when clinically indicated. Investigators or the Sponsor can also withdraw subjects from the clinical study if deemed to be necessary.

Reasons for discontinuing study drug include:

- Subject request (i.e., consent withdrawal)
- Non-compliance with the study drug or study schedule
- Lost to follow-up
- Occurrence of AEs, including TEAE and laboratory abnormalities, not compatible with the continuation of subject participation in the study, in the Investigator's opinion, or unacceptable to the subject to continue, including but not limited to the following:
  - Serious immediate-type allergic manifestations including anaphylactic reaction
  - Serious worsening of asthma considered related to study drug administration
  - Diagnosis of a malignancy (except curatively treated in situ cervical carcinoma, squamous cell carcinoma [Bowen's disease], or basal cell carcinoma)

- Opportunistic infections such as but not limited to active tuberculosis (TB) and other infections whose nature or course suggest an immune-compromised or immune-suppressed status
- Any serious infection or any severe infection requiring treatment with parenteral antibiotics or oral antibiotics/antivirals/antifungals for >2 weeks considered related to study drug administration
- Confirmed or suspected COVID-19 infection (temporary discontinuation may be acceptable; for instructions on resuming study drug administration, see Section 8.3.2).
- Pregnancy (see Section 8.3.1)
- Use of non-permitted concurrent therapy (as specified in Section 9.6.3, unless discussed and agreed upon with the Investigator and Medical Monitor)
- Use of systemic rescue therapy (as specified in Section 9.6.2)
- Treatment failure (subjects who relapse may be eligible to re-enroll in the LTE study)
- Investigator request
- Sponsor request, including any of the above criteria

The reason(s) for withdrawal will be documented in the electronic case report form (eCRF). Subjects who have been enrolled and treated will not be replaced by another subject.

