Subjects who prematurely discontinue study drug for reasons other than relapse will be encouraged to complete the scheduled study visits. These subjects will only be eligible for continued treatment with nemolizumab in the LTE study if they continue with study visits through Week 24.

When a subject is withdrawn from the study, he/she will be fully assessed whenever possible, and followed according to guidelines presented in Section 10.3.1 (ET Visit).

Reasonable efforts will be made to contact subjects who are lost to follow-up. These efforts must be documented in the subject's file.

The Sponsor has the right to terminate the study at any time in case of SAEs or if special circumstances concerning the investigational product or the company itself occur, making further treatment of subjects impossible. In this event, the Investigator(s) will be informed of the reason for study termination.

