COVID-19=coronavirus disease 2019; JAK=Janus kinase; NK=neurokinin; PDE-4=phosphodiesterase-4; PN=prurigo nodularis; PUVA=psoralen+ultraviolet A; UVB=ultraviolet B.

If a prohibited therapy becomes necessary for the safety of the subject, the Investigator should notify the Medical Monitor and discuss possible alternatives. If a subject receives a prohibited therapy during the clinical study (e.g., inadvertent short-term use), the Investigator should also notify the Medical Monitor and discuss whether or not it is acceptable for the subject to continue receiving the study drug.

It is recommended that all subjects should be up to date with respect to standard of care vaccinations as defined by the local guidance. For subjects who have vaccination planned during the study, it will be determined after consultation with the treating physician, whether the administration of vaccine can be postponed until after the end of study without compromising the health of the subject. See also Section 9.6.1.

Vaccinations during the study and follow-up period are not permitted, with the exception of the specified non-live vaccines in Section 9.6.1.

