### 14.3 Efficacy Analysis

A summary based on observed case (OC) will be provided for all primary and secondary efficacy endpoints. For OC, no data will be imputed.

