8.3. Missing Data

When analyses are not based on OC, the primary method to impute the missing values will be as follows:

Continuous Endpoints: For continuous secondary endpoints during treatment period, the MMRM approach will be used to handle the missing data.

Binary Endpoints: For binary secondary endpoints during treatment period, missing data will be imputed to failure.

Adverse events and concomitant medications/procedures: Missing assessment times will have imputed times for the purposes of assessing treatment emergence for AEs or classifying medications/procedures into prior/concomitant. However, the assessment date and time (start date, stop date, and time if collected from CRF) without imputation will be presented in the listings.

For the start of a concomitant medication/procedure or AE:

- Only the year is reported: If the subject received the first study drug dose in the year reported, then the date of the first dose of study drug will be used as the start date; otherwise, January 1 of the year reported will be used as the start date.
- The month and year are reported: If the subject received the first study drug in the month and year reported, then the date of the first dose of study drug will be used as the start date; otherwise, the first day of the month and year will be used as the start date.
- The time is collected but missing: If the start date is the same as the date the subject started receiving study drug, then the time of the first dose of study drug will be used as the start time; otherwise, 00:00 will be used as the start time.

For the end of a concomitant medication/procedure or AE:

- Only the year is reported: The earlier between December 31 of the year reported and the date of the last study contact with the subject will be used as the stop date.
- The month and year are reported: The earlier between the last date of the month and year reported and the date of the final contact with the subject will be used as the stop date.
- The time is collected but missing: 23:59 (or 23:59:59 if collected up to seconds) will be used as the stop time.

This document is confidential.

If an AE has the start date completely missing and the stop date on/after the first dose date of study drug, this AE will be considered as treatment emergent (TEAE).

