10.2. Secondary Efficacy Endpoints

The following secondary endpoints are to be analysed at the scheduled visits:

Endpoint	Analysis Visit	Analysis to be done on which Population	Statistical Tests
Proportion of subjects maintaining IGA success at each scheduled visit	Baseline, Week 4, Week 8, Week 12, Week 16, Week 20, Week 24	On the ITT and Per-Protocol Population	CMH
Proportion of subjects with increase in IGA ≥ 2 points from baseline at each scheduled visit	Baseline, Week 4, Week 8, Week 12, Week 16	On the ITT and Per-Protocol Population	CMH
Proportion of subjects with increase in PP NRS score ≥ 4 points from baseline at each scheduled visit	Baseline, Week 4, Week 8, Week 12, Week 16, Week 20, Week 24	On the ITT and Per-Protocol Population	CMH
Absolute and percent change from baseline in PP NRS at each scheduled visit	Baseline, Week 4, Week 8, Week 12, Week 16, Week 20, Week 24	On the ITT and Per-Protocol Population	ANCOVA
Absolute and percent change from baseline in PP NRS at each scheduled visit	Baseline, Week 4, Week 8, Week 12, Week 16, Week 20, Week 24	On the ITT	MMRM

This document is confidential.

Endpoint	Analysis Visit	Analysis to be done on which Population	Statistical Tests
Absolute and percent change from baseline in SD NRS at each scheduled visit	Baseline, Week 4, Week 8, Week 12, Week 16, Week 20, Week 24	On the ITT and Per-Protocol Population	ANCOVA
Absolute and percent change from baseline in SD NRS at each scheduled visit	Baseline, Week 4, Week 8, Week 12, Week 16, Week 20, Week 24	On the ITT	MMRM
Change from baseline in DLQI at each visit	Baseline, Week 16, Week 24	On the ITT Population	ANCOVA

Abbreviations: CMH=Cochran-Mantel-Haenszel; DLQI=Dermatology Life Quality Index; IGA=Investigator Global Assessment; PP=Peak Pruritus; SD=Sleep Disturbance.

Binary secondary efficacy endpoints will be analyzed using a Cochran-Mantel-Haenszel test adjusted for dosing regimen based on OC and imputation with missing efficacy response considered as the non-responder (i.e., IGA success) and missing relapse response considered as a relapse (i.e., increase in PP NRS or IGA). The estimate of treatment unadjusted and strata-adjusted differences with the corresponding two-sided 95% confidence intervals, and p-values from the CMH test will be presented.

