10.2.1. Investigator's Global Assessment (IGA)

The IGA is a 5-point scale used by the Investigator or trained designee to evaluate the global severity of PN and the clinical response to a treatment (see [Table 10-1](#)).

Table 10-1: Investigator Global Assessment Scale

0	Clear	No nodules
1	Almost Clear	Rare palpable pruriginous nodules
2	Mild	Few palpable pruriginous nodules
3	Moderate	Many palpable pruriginous nodules
4	Severe	Abundant palpable pruriginous nodules

IGA treatment success is defined as 0 (clear) or 1 (almost clear) on the IGA scale.

IGA will be collected at Baseline/Day 1, Week 4, Week 8, Week 12, Week 16, Week 20, Week 24 and Early Termination or any unscheduled visit. In case of missing assessment at Baseline, the last available assessment prior study drug administration will be considered as Baseline.

IGA will be summarized as a categorical and continuous variable at each analysis visit. Absolute change from Baseline for the IGA score will also be presented in the summary on the ITT and Per-Protocol Population.

The proportion of subjects maintaining IGA success and subjects with increase in IGA ≥ 2 points from baseline will be summarized on the ITT based on OC. The estimate of treatment unadjusted and strata-adjusted differences with the corresponding two-sided 95% confidence intervals, and p-values from the CMH test will be presented.

The analysis will be repeated:

- on Per-Protocol Population, based on OC
- on ITT population, imputing missing values with non-responder imputation

Line plot for proportion of subjects maintaining IGA success and proportion of subjects with increase in IGA ≥ 2 points from baseline, both using non-responder imputation, will be for the ITT Population.

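### The binary secondary analyses replace only missing values, so an IGA of 0 or 1 observed after prohibited PN therapy or after stopping study drug counts as maintained success

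*SAP*

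**What the plan says.** **Secondary endpoints.** SAP 10.2 analyses the binary endpoints "based on OC and imputation with missing efficacy response considered as the non-responder (i.e., IGA success"), and treats a missing relapse outcome as a relapse. SAP 8.3 gives the general rule: "For binary secondary endpoints during treatment period, missing data will be imputed to failure". SAP 10.2.1 repeats the IGA analysis "on ITT population, imputing missing values with non-responder imputation". The observed-case (OC) version leaves data as recorded; Protocol 14.3 says "For OC, no data will be imputed". Success carries no condition on treatment or medication: "IGA treatment success is defined as 0 (clear) or 1 (almost clear) on the IGA scale".

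**Primary endpoint.** SAP section 7 names two intercurrent events, treatment discontinuation and prohibited medication, and censors later data after either. The section is introduced for the primary endpoint, and its only estimand table (7-2) is titled for it. Protocol 14.3.1 likewise censors users of prohibited therapy from the primary analysis.

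**Who stays under observation.** After prohibited therapy, Protocol 9.6.3 has the Investigator and Medical Monitor "discuss whether or not it is acceptable for the subject to continue receiving the study drug". Protocol 8.3 adds: "Subjects who prematurely discontinue study drug for reasons other than relapse will be encouraged to complete the scheduled study visits". It makes later access to the LTE study conditional on attending through Week 24. SAP 8.4 places all visits, including unscheduled and early termination visits, by study day, with no on-treatment filter.

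**The concern.** The secondary endpoints are meant to show whether response is kept or lost once nemolizumab is withdrawn. Two subjects who have both lost some control can be scored in opposite ways. One takes a banned topical corticosteroid and is seen at IGA 1: a maintained success. The other misses the visit: a failure. The first result may reflect the steroid, and the primary analysis stops following that subject at the last assessment before the steroid. The secondary tables and line plots would then answer a different question from the primary analysis, without the SAP saying so. At about 20 subjects per arm, a few such cases are enough to shift a reported rate visibly.

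**Working it through.** The plan states no figure on this point, so there is nothing to reproduce. The check compares the rules and then works out the weight of one subject.

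**Step 1: who can be affected.** Relapse is a PP NRS rise of at least 4 or an IGA rise of at least 2 from baseline. Entry requires IGA 0 or 1. From baseline IGA 0, reaching IGA 2 is already relapse. Losing IGA success without relapsing on IGA therefore requires baseline IGA 1 and a move to IGA 2, with PP NRS up by less than 4. For the two increase endpoints, the affected subject is one whose worsening is held below threshold by other therapy.

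**Step 2: apply the rules to three hypothetical subjects, all with baseline IGA 1.**

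| Subject | Primary analysis | OC, Week 16 | Imputed ITT, Week 16 |
|---|---|---|---|
| A: IGA 2 at Week 8, then topical corticosteroid, IGA 1 at Week 16 | Censored before the steroid | Success; no IGA increase of 2 | Same as OC |
| B: IGA 2 at Week 8, no other therapy, Week 16 missed | No relapse recorded at Week 8 | Not counted | Failure; relapse |
| C: IGA 3 at Week 8 | Event; exits the study | Not counted | Failure; relapse |

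A and B differ only in therapy and attendance. C shows that subjects who relapse do not cause the problem.

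**Step 3: look for a rule that removes A's Week 16 value.** None of SAP 8.3, 8.4, 10.2 or 10.2.1 refers to section 7. SAP 8.2 ends the treatment period of early discontinuers no later than 28 days after the last dose, and 8.3 limits imputation to the treatment period. That makes the reach of the imputation unclear but does not exclude later observed values.

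**Step 4: size.** SAP 4.3 and Protocol 14.1 expect about 40 subjects, so 40/2 = 20 per arm and one subject is 1/20 = 5 points. SAP 4.1 says about 100, so 100/2 = 50 per arm and one subject is 1/50 = 2 points. With k_N and k_P affected subjects on nemolizumab and placebo:

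reported difference = difference with these subjects scored as failures + (k_N − k_P)/n

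For a net imbalance of 1 to 4 subjects (assumed), the shift is 5 to 20 points at n = 20 and 2 to 8 points at n = 50, in either direction.

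**Step 5: illustration only.** The documents give no response rates. Assume 80% vs 40% success when these subjects count as failures, with all affected subjects on placebo. Fisher's exact test is used, unstratified, unlike the planned CMH test.

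| Per arm | k_P | Counts | Difference | p |
|---|---|---|---|---|
| 20 | 0 | 16 vs 8 | 40 points | 0.0225 |
| 20 | 1 | 16 vs 9 | 35 points | 0.0484 |
| 20 | 2 | 16 vs 10 | 30 points | 0.0958 |
| 20 | 4 | 16 vs 12 | 20 points | 0.3008 |
| 50 | 4 | 40 vs 24 | 32 points | 0.0016 |

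**The case against.** The strongest reply is that the route is narrow.

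- **Exit at relapse.** Protocol 7.1 and 9.6.2 take relapsing subjects out of the study, so their later visits are missing and score as failures. This stands. A reader might infer that a placebo subject with a full flare could be steroid-treated back to success; the exit rule does not allow that reading. Only sub-threshold worsening remains.
- **Stopping rule for banned therapy.** A reader might infer that Protocol 8.3 covers only systemic rescue. It also lists non-permitted concurrent therapy in general, unless continuation is agreed with the Medical Monitor, and the example in 9.6.3 is inadvertent short use. This narrows the route but does not close it, since a subject taken off study drug may still attend visits.
- **Other conventional therapy.** That sentence in Protocol 8.3 concerns subjects leaving participation. It is no evidence of treated on-study data.
- **Per-protocol repeats.** Prohibited therapy is a listed major-deviation category, and all three binary endpoints have a per-protocol analysis. Exclusion is decided case by case at the blind data review meeting (BDRM), and that analysis is OC only. The mitigation is partial and leaves the ITT tables as they are.
- **Table 7-1 says any data.** If that wording was meant to reach the secondary endpoints, the SAP does not say so, nor whether removed values become failures or stay missing.
- **Treatment policy.** Using all observed data is a legitimate strategy if declared and justified. The SAP declares no strategy for the secondary endpoints.

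**Conclusion.** The point holds in a limited form. For subjects who worsen below the relapse threshold, use prohibited PN therapy or stop study drug, and remain on visits, the written rules count an observed IGA of 0 or 1 as maintained success, and an increase below threshold as no relapse, in both ITT analyses. The same unfiltered values enter the OC-based ANCOVA and, for PP NRS and SD NRS, the MMRM.

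The weight is 5 points per affected subject at 20 per arm, or 2 points at 50 per arm. How many subjects will be affected is unknown. A reader might infer that the placebo arm will look better and the treatment difference will shrink. That is plausible, because loss of response is expected there, but the documents do not establish it; the direction depends on which arm has more such subjects. The 80% vs 40% illustration shows sensitivity and predicts nothing. This should be corrected because the change is small. It does not affect the primary analysis.

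**What to change.** In SAP 8.3 and 10.2, for the imputed ITT analysis of the three binary endpoints, set visits to non-response (IGA success) or relapse (IGA or PP NRS increase) after either of these events:

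- the start of a prohibited medication that could affect PN or itch, classified blind at the BDRM; or
- permanent study-drug discontinuation for lack of efficacy.

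Keep the as-observed analysis as supportive. State that values after discontinuation for other reasons are used as observed. For PP NRS, SD NRS and DLQI, add a sensitivity analysis that excludes values after these two events; making that exclusion the main analysis is more debatable and is not needed here.

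The cost is SAP wording, one derivation flag and a blinded classification. Concomitant therapies and withdrawal reasons are already recorded (Protocol 9.6 and 8.3). The documents do not say that the indication for each medication is collected, which is why the classification belongs at the BDRM. The downside is that a few observed values move to a supportive table.

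Separately, the protocol contradicts itself on rescue. Section 8.3 lists "Use of systemic rescue therapy (as specified in Section 9.6.2") as a reason to stop study drug, section 9.6.2 permits no rescue therapy, and section 10.3.2 provides unscheduled efficacy visits for subjects who need it. These passages must be reconciled.

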**Table 3. Treatment Summary**

LTE Lead-in Study	Lead-in Study Assigned Treatment	Dose Q4W for 24 weeks a
RD.06.SPR.202699	Nemolizumab 30 mg (1 injection)	Blinded Nemolizumab 30 mg (1 injection)
	Nemolizumab 2 × 30 mg (2 injections)	Blinded Placebo (1 injection)
		Blinded Nemolizumab 2 × 30 mg (2 injections)
		Blinded 2 × Placebo (2 injections)

Abbreviation: LTE = long-term extension; Q4W = every 4 weeks.

aDose will be assigned based on dose received in LTE lead-in study.

Clinical assessments will occur according to the Schedule of Assessments in the protocol through the Week 24 visit.

If a subject meets the criteria for relapse at any point, the subject will exit the study and re-enter the LTE study (see [Figure 2](#)). Subjects who exit the study before Week 24 should complete an early termination (ET) visit. Subjects who complete the study through Week 24 are eligible to re-enroll in the LTE study.

Subjects who prematurely discontinue study drug for reasons other than relapse will be encouraged to complete the scheduled study visits. These subjects will only be eligible for re-enrollment in the LTE study if they continue with study visits through Week 24.

Subjects who discontinue the study for reasons other than relapse before Week 24 or who will not continue nemolizumab treatment in the LTE study should complete a follow-up visit, 12 weeks ( $\pm 7$  days) after the last study drug injection.

[figure not shown]

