### 9.6.2     Rescue Therapy

Rescue therapies are not permitted in this study. Subjects enrolled in this study have demonstrated a clinical response to nemolizumab; therefore, if a subject experiences relapse, they will be discontinued from this study and may be eligible to continue to receive nemolizumab by re-enrolling in the LTE study (see [Figure 2](#)).

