5.2. Secondary Efficacy Endpoints

The secondary efficacy endpoints are as follows:

- Proportion of subjects with increase in PP NRS score ≥ 4 points from baseline at each scheduled visit
- Proportion of subjects maintaining IGA success, defined as IGA score of 0 (clear) or 1 (almost clear) at each scheduled visit
- Proportion of subjects with increase in IGA ≥ 2 points from baseline at each scheduled visit
- Absolute and percent change from baseline in PP NRS at each scheduled visit
- Absolute and percent change from baseline in Sleep Disturbance Numeric Rating Scale (SD NRS) at each scheduled visit
- Change from baseline in DLQI at Week 16 and Week 24

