10.1. Primary Efficacy Endpoints

10.1.1. Primary Analysis of Primary Efficacy Endpoint

The primary endpoint is the time to relapse which is defined as meeting at least 1 of the following criteria:

- Increase in (weekly average of the) PP NRS score ≥ 4 points from baseline
- Increase in IGA score ≥ 2 points from baseline;

For primary endpoint, any subjects with missing data for PP NRS and IGA Score both at visit will be censored at the respective timepoint. If any one of PP NRS or IGA Score data is available for the visit, calculation for primary endpoint will be made using available results. If a subject has taken prohibited medication at any point of time during treatment period, then subject will be censored at the respective visit.

The primary endpoint will be analyzed using Cox proportional hazard model with treatment group, dosing regimen as a factor, and baseline PP NRS score and IGA score as covariates on ITT population. The estimated hazard ratio and the corresponding 95% CI will be presented. A supportive analysis also will be performed using Per-Protocol Population.

Kaplan-Meier survival plots will also be presented for time to relapse. The median time, 25th and 75th quantiles along with corresponding CI will be presented using ITT/PP.

Censoring rule for primary endpoint variable is as follows:

Situation	Date of Progression or Censoring	Outcome
Relapse as described	Date of Relapse	Event
Subject withdrawn without relapse	Date of last efficacy assessment (PP NRS and IGA) prior to withdrawal	Censored
Treatment Discontinuation	Date of last efficacy assessment (PP NRS and IGA) prior to Treatment Discontinuation	Censored
Prohibited medication without relapse	Date of last efficacy assessment (PP NRS and IGA) prior to prohibited medication	Censored
Completes the study without relapse	Date of Week 24 completion	Censored
No Efficacy assessment	Date of study Day 1	Censored

This document is confidential.

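### The missing-as-failure repeat analyses count a relapse on one criterion as failure on the other at every later analysed visit, and no planned output shows documented relapse by criterion

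*SAP*

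**What the plan says.** SAP 10.1.1 describes the primary endpoint as "the time to relapse which is defined as meeting at least 1 of the following criteria", namely the PP NRS or the IGA threshold. Protocol 7.1, after Table 3, states: "If a subject meets the criteria for relapse at any point, the subject will exit the study and re-enter the LTE study". Protocol 9.6.2 agrees: "if a subject experiences relapse, they will be discontinued from this study".

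The lesion criterion is also a secondary endpoint in its own right (SAP 5.2): "Proportion of subjects with increase in IGA ≥ 2 points from baseline at each scheduled visit". The itch criterion has a matching endpoint, and maintained IGA success (score 0 or 1) is a third.

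The exit score is collected. SAP 10.2.1 states: "IGA will be collected at Baseline/Day 1, Week 4, Week 8, Week 12, Week 16, Week 20, Week 24 and Early Termination". SAP 8.4 assigns the early-termination visit to an analysis window by study day, and no rule uses that score in later windows.

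The binary endpoints are analysed twice. SAP 10.2.1 says the IGA endpoints "will be summarized on the ITT based on OC", with the CMH difference, interval and p-value. SAP 10.2.2 treats PP NRS in the same way. Both sections then repeat the ITT analysis with imputation. SAP 8.3 gives the general rule: "For binary secondary endpoints during treatment period, missing data will be imputed to failure". SAP 10.2 gives the direction for the worsening endpoints: "missing relapse response considered as a relapse (i.e., increase in PP NRS or IGA". The imputed outputs are Tables 14.2.2.1.6, 14.2.2.1.11 and 14.2.2.2.6. All three line plots of these proportions use the imputed version only.

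**The concern.** The trial asks how long control of lesions and of itch lasts once nemolizumab is withdrawn, so the two separate worsening endpoints carry information that the composite primary does not. The imputation takes no account of which criterion ended participation, although the other criterion's status at exit is normally known. In a withdrawal trial most relapse exits are expected on placebo, so the imputed failures fall mainly there. Imputing failure is then not conservative: it can create a treatment difference on lesions that comes only from itch exits, or the reverse.

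Monitoring is also unequal. PP NRS is recorded daily and averaged weekly, while IGA is scheduled at six post-baseline visits. Itch has more occasions to trigger exit first, so overstatement of lesion relapse is the more plausible direction.

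**Working it through.** The plan has no figure to reproduce. SAP 4.3 reports no formal sample size calculation, and neither document gives relapse rates or a split by criterion. All rates below are assumptions.

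**Step 1. Trace the rules by type of exit.** Let *a*, *b*, *c* and *d* be the shares of an arm that leave for itch only, IGA only, both criteria, or another reason without later visits. All exits are taken to precede the last analysed window.

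| Exit | IGA ≥2 met at exit | IGA ≥2 imputed later | PP NRS ≥4 met at exit | PP NRS ≥4 imputed later |
|---|---|---|---|---|
| Itch only (*a*) | no | yes | yes | yes |
| IGA only (*b*) | yes | yes | no | yes |
| Both (*c*) | yes | yes | yes | yes |
| Other (*d*) | no | yes | no | yes |

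Imputed proportion, either endpoint = *a* + *b* + *c* + *d*. Documented IGA increase = *b* + *c*. Documented PP NRS increase = *a* + *c*. An itch-only subject who leaves with IGA 0 or 1 also becomes a failure for maintained IGA success.

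**Step 2. Two assumed placebo splits.**
- *a* 30%, *b* 20%, *c* 10%, *d* 5%: imputed 65% on both endpoints; documented IGA 20 + 10 = 30%; documented PP NRS 30 + 10 = 40%.
- *a* 40%, *b* 5%, *c* 5%, *d* 10%: imputed 60% on both; documented IGA 5 + 5 = 10%; documented PP NRS 40 + 5 = 45%.

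**Step 3. Range over the itch-only share *s*.** Assume relapse of 60% on placebo and 10% on nemolizumab, with no other exits. Documented IGA increase = relapse × (1 − *s*).
- *s* = 0.5: 0.60 × 0.5 = 30% and 0.10 × 0.5 = 5%, a difference of 25 points.
- *s* = 0.7: 0.60 × 0.3 = 18% and 0.10 × 0.3 = 3%, 15 points.
- *s* = 0.9: 0.60 × 0.1 = 6% and 0.10 × 0.1 = 1%, 5 points.
- Imputed, for any *s*: 60% and 10%, 50 points.

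**Step 4. Limiting case.** Suppose no subject's IGA worsens and itch relapse is 50% on placebo and 10% on nemolizumab. The imputed IGA ≥2 rates are 50% and 10%, a 40-point difference with no documented lesion relapse in either arm. The chance of two-sided p<0.05 is Φ[(*d* − 1.96·SE0)/SE1], where *d* is here the difference in rates. With 20 per arm, SE0 = √(0.30 × 0.70 × 2/20) = 0.145 and SE1 = √(0.50 × 0.50/20 + 0.10 × 0.90/20) = 0.130, so (0.40 − 0.284)/0.130 ≈ 0.89 and the chance is about 81%. A simulated stratified CMH test (two strata split 70/30, 10,000 runs) gave 83%. From 30% vs 10% up to 70% vs 20%, the formula gives 35% to 92%. SAP 4.1 states about 100 subjects where SAP 4.3 and Protocol 14.1 state about 40; at 50 per arm the range is 71% to over 99%.

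**Step 5. Does OC supply the missing figure?** No. After the exit window, relapsers are in neither numerator nor denominator. With 50% exits, 10 of 20 placebo subjects remain, and none of them has yet left for relapse. A later OC proportion therefore shows only new worsening among those still in the study and understates relapse to date.

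**The case against.** - **OC comes first.** This stands. The OC tables do not carry the artefact, and a reader who infers that every reported lesion or itch result is contaminated goes too far. But OC loses the relapsers (Step 5), and the line plots show only the imputed version.
- **Missing-as-failure is prespecified and defensible.** Protocol 14.3.2 contains it, and counting any relapse as failure is a legitimate composite. Protocol 5.1 and 5.3 also describe itch as driving lesions, so IGA at the moment of an itch relapse may understate later lesion return. This is a good reason to keep the rule. It does not justify presenting the result under a name that refers to one criterion alone; the SAP's estimand table covers only the primary endpoint.
- **The split can be recovered from listings.** Listings 16.2.6.1 to 16.2.6.3 would show it subject by subject, but a listing gives no comparison between arms.
- **Re-entry wording.** The main design text in Protocol 7.1 says only that relapsers may be considered for re-entry. That softens re-entry, not exit.

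**Conclusion.** The concern holds for the imputed repeat analyses of the three binary endpoints and their line plots. After a relapse exit these results drift towards 'any relapse or missing' and no longer separate lesions from itch. The primary time-to-relapse analysis is unaffected.

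Three stronger readings are not supported:
- A reader might infer that the imputed endpoints duplicate the primary. They do not: SAP 10.1.1 censors withdrawal, treatment discontinuation and prohibited medication, whereas the imputation counts the resulting missing values as failures.
- A reader might infer that lesions will appear to return exactly as early as itch. The exit window keeps an observed score; imputation starts at the next analysed window.
- A reader might take the gap of 60% against 30% to 6% as error against the truth at Week 24. It is the distance from documented status at exit, under assumed rates. The SAP 10.2 table lists the IGA ≥2 endpoint only to Week 16, although SAP 5.2 promises every scheduled visit.

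The size depends on the split by criterion, which the documents do not give. If nearly all relapsers met both criteria at exit, the effect of relapse exits would be small.

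**What to change.** 1. In SAP 10.2, 10.2.1 and 10.2.2, keep the missing-as-failure analysis but label it as a composite in tables and plots, for example 'IGA increase ≥2, relapse on any criterion, or missing'. Label the PP NRS and IGA-success outputs likewise.
2. Beside it, add a criterion-specific row for all three binary endpoints. After a relapse exit, a criterion met at or before exit counts as failure from then on, and the other keeps its observed early-termination status. For IGA success, an itch-only exit keeps the early-termination result. All other missing values, including a missing early-termination score, stay as failure.
3. Add one table of first relapse by criterion (itch only, IGA only, both) per arm.
4. Reconcile SAP 5.2 with the SAP 10.2 table so that the IGA ≥2 and PP NRS ≥4 endpoints are shown at the same visits.

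The cost is SAP wording, extra rows and one table; no new data are needed, and SAP 17 does not treat changes to the table list as deviations. The downside is that the criterion-specific row misses lesion worsening that might follow an itch relapse, which is why the composite row stays beside it.
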